9 EVALUATION OF SAFETY

All enrolled subjects who have received SOF/LDV will be evaluated for safety. Safety will be assessed by physical examination, vital signs, hematology, and chemistries. The severity of signs, symptoms, and AEs will be determined by using the 2014 DAIDS Table for Grading the Severity of Adult and Pediatric Adverse Events, with edits made to allow for clinical center normal values.

9.1 Follow-up of Abnormal Laboratory Test Values

In the event of unexplained abnormal laboratory test values, the tests should be repeated as soon as possible and followed up until they have returned to the normal range and/or an adequate explanation of the abnormality is found. If a clear explanation is established it should be recorded.

9.2 Criteria for Premature Withdrawal and Stopping Rules

Subjects have the right to withdraw from the study at any time for any reason. Subjects who withdraw early or who are terminated from study by the Investigator will not be replaced unless they have received no study drugs. In addition to the criteria for stopping subject treatment described in section 8.9, the Investigator or designee also has the right to withdraw subjects from the study for any of the following:

1. Participant's desire to leave study.
2. Pregnancy or breastfeeding.
3. Participant's non-compliance. If a subject misses 5 or more total study visits or > 3 weeks of study drug, the subject will be removed from the protocol by the study team.
4. Termination of study.
5. Development of a medical condition that in the opinion of the Investigator, it is in the subject's best interest to discontinue study drug even if criteria requiring drug discontinuation have not been met.
6. Request of the primary care provider or Investigator if s/he thinks the study is no longer in the best interest of the subject.
7. Clinical reasons believed life threatening by the physician.

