4.2.1 Efficacy Population

The primary analysis population for efficacy analysis will be defined as all participants who received at least one dose of study drug.

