4.3 Data Handling Conventions

Missing data can have an impact upon the interpretation of the trial data. Other than the endpoints discussed below, values for missing data will not be imputed.

For the analysis of post-baseline categorical efficacy endpoints, if a data point is missing and is preceded and followed in time by values that are deemed successes, then the missing data point will be termed a success; otherwise the data point will be termed a failure.

Any subject with missing data due to premature discontinuation of the study medication will be considered a failure at the time points on, or following, the date of discontinuation. If no HCV RNA values are obtained after the last dose of study medication, the subject will be considered a treatment failure for the SVR endpoints.

Where appropriate, safety data for subjects that did not complete the study will be included in summary statistics. For example,

- If a subject received study medication, the subject will be included in a summary of adverse events according to the treatment received; otherwise, if the subject is not dosed then they will be excluded from the summary.
- If safety laboratory results for a subject are missing for any reason at a time point, the subject will be excluded from the calculation of summary statistics for that time point. If the subject is missing a pre-dose value, then the subject will be excluded from the calculation of summary statistics for the pre-dose value and the change from pre-dose values.

Values for missing vital signs data will not be imputed; however, a missing Day 0 result will be replaced with a screening result, if available.

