4.4 Efficacy Analyses

4.4.1 Primary Analysis

The primary efficacy endpoint is SVR₁₂ (HCV RNA <LLOQ 12 weeks after cessation of therapy.)

There is no active comparator group for this study (as in most clinical trials with all oral therapies in these populations).

In the primary efficacy analysis, an exact Clopper-Pearson 95% confidence interval will be computed for the SVR₁₂ rate.

The primary analysis will be performed after all enrolled subjects have been followed through 12 weeks post-treatment or discontinued from study.

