7.10 Early Termination and Early Treatment Discontinuation

Participants who elect to discontinue study drugs prior to treatment completion for medical or personal reasons will be given the option of being followed up at least every 12 weeks for safety and research labs until the end of the study. The participant should have an end of treatment visit scheduled as soon as possible after all therapy is discontinued. Participants with undetectable HCV RNA at the end of treatment should continue to follow the scheduled SVR visits following the date of their last dose of therapy.

For the prospective arm, participants who have detectable HCV RNA at the end of treatment or who relapse post-treatment will be asked to return for visits to determine the persistence of any HCV populations with treatment-emergent substitutions conferring resistance to sofosbuvir. Samples collected will be used to determine the durability of response or the dynamics of any changes in resistance conferring mutations. The reason for any early termination should be documented.

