8.7 Dose Modifications/Toxicities

Maximal suppression of HCV replication is most likely accomplished by sustained delivery of antiviral agents at their current recommended doses. Dose reduction, however, would compromise this goal and predispose to the emergence of drug-resistant viral variants. Hence, no dose reduction will be allowed for SOF/LDV. If SOF/LDV is stopped due to toxicity, it must not be restarted.

If treatment with study drug is interrupted for \leq 5 consecutive days for reasons other than drug toxicity (such as discontinuation due to GFR $<$ 30), treatment can be reinitiated and the subject can remain in the trial. However, if treatment is interrupted for $>$ 5 days and/or if study drug is interrupted due to drug toxicity, treatment with study drug should be discontinued.

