8.9 Criteria Requiring Discontinuation of SOF/LDV

Subjects will be considered treatment failures and will discontinue SOF/LDV if they meet any of the following criteria while taking study drugs:

- Plasma HCV RNA greater than LLOQ after 2 prior consecutive HCV RNA values less than the LLOQ
- Greater than a $1 \log_{10}$ increase in plasma HCV RNA from nadir
- Less than a $2 \log_{10}$ decline in HCV RNA after 4 weeks of treatment

If any of these should occur in a subject who is currently on study drugs, the subject should return within one week for a confirmatory test. If the confirmatory test also meets the same criteria, the subject will be considered a treatment failure and should be discontinued from therapy. Participants will be referred for other treatment options. The anticipated clinical impact of discontinuation should be discussed in advance if possible, particularly if discontinuation is thought to pose a risk to the overall clinical wellbeing of the subject. Those who are discontinued will continue to follow the general study schedule of assessments unless unwilling to do so, in which case they may be seen at least every 12 weeks for safety and research labs until the end of the study. Subjects will be followed closely for resolution of active laboratory abnormalities or adverse events that are considered related to the study agents prior to starting the revised schedule.

Subjects who meet any of the following laboratory criteria must stop all study medication(s):

- Any Grade 3 or greater rash associated with constitutional symptoms
- Any Grade 4 event assessed as possibly, probably, or definitely related to treatment with SOF or LDV

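### Section 9.2 item 3 removes a participant who misses more than 3 weeks of drug without saying that SVR follow-up continues, so a participant who cleared HCV could be scored an SVR12 failure

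*Combined protocol and SAP*

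**What the plan says.** All references are to the combined protocol and SAP.

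- **Section 9.2, item 3.** If a participant "misses 5 or more total study visits or > 3 weeks of study drug, the subject will be removed from the protocol". The lead-in to the list gives the investigator the right to withdraw subjects from the study, and presents this as additional to the treatment-stopping criteria of 8.9. Dosed participants who leave are not replaced.
- **Section 7.10** (headed for both early termination and early treatment discontinuation). "Participants with undetectable HCV RNA at the end of treatment should continue to follow the scheduled SVR visits", timed from the last dose.
- **Section 8.7.** Drug is stopped if it is interrupted for more than "5 days and/or if study drug is interrupted due to drug toxicity, treatment with study drug should be discontinued". Nothing there ends follow-up.
- **Section 8.9**, in the paragraph on confirmed virologic failure. "Those who are discontinued will continue to follow the general study schedule of assessments unless unwilling to do so".
- **Section 4.2.1.** The efficacy population is "all participants who received at least one dose of study drug".
- **Section 4.3.** A missing categorical efficacy value counts as a success only if successes come both before and after it; "otherwise the data point will be termed a failure". In addition, "Any subject with missing data due to premature discontinuation of the study medication will be considered a failure" from the date of discontinuation on.
- **Section 4.4.1.** The primary analysis is an exact Clopper-Pearson 95% interval for the SVR12 rate, run once all enrolled subjects have been "followed through 12 weeks post-treatment or discontinued from study".

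**The concern.** Stopping study drug and leaving the study are different events. For an endpoint measured 12 weeks after the last dose, the difference decides whether the result is observed or imputed. Item 3 is triggered by missed drug, yet its stated consequence is removal from the protocol. It does not say that the post-treatment HCV RNA is still to be collected, and it does not say whether the three weeks are cumulative.

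Poor adherence does not rule out clearance. If a site applies item 3 as written to someone who in fact cleared the virus, a success that could have been measured at an already scheduled visit enters the primary analysis as a failure. Sites may also apply the item differently, because 7.10 gives reason to keep the same person in follow-up.

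**Working it through.** **Step 1. What happens to one participant under the literal reading.** Take a prospective participant who misses more than 3 weeks of drug, is undetectable when drug stops, and would have been below the LLOQ 12 weeks later.

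| Stage | Item 3 read literally | 7.10 applied |
|---|---|---|
| Study drug | ends | ends |
| HCV RNA 12 weeks after last dose | not collected | collected |
| 4.3 status of SVR12 | missing, with no later value to bracket it: failure | observed: success |
| 4.2.1 denominator | included | included |

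The two columns differ only in whether the sample is taken. The bracketing rule in 4.3 cannot rescue the value, because no later success exists once follow-up has ended. If the value is instead treated as missing because drug was stopped early, 4.3 again gives failure.

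**Step 2. The plan's own figures.** Section 4.1, Table 1 gives exact limits for 50 participants (its footnote names 25, but the entries are those for 50, as the text says). For x successes out of n, the lower limit is the 2.5% quantile of Beta(x, n − x + 1), which for x = n is 0.025^(1/n). The upper limit is the 97.5% quantile of Beta(x + 1, n − x), or 1 when x = n.

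| x of 50 | Table 1 | Recomputed |
|---|---|---|
| 50 | 0.929–1 | 0.9289–1 |
| 48 | 0.863–0.995 | 0.8629–0.9951 |
| 46 | 0.808–0.978 | 0.8077–0.9778 |
| 44 | 0.757–0.955 | 0.7569–0.9547 |
| 42 | 0.709–0.928 | 0.7089–0.9283 |
| 40 | 0.663–0.900 | 0.6628–0.8997 |

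All six entries reproduce.

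**Step 3. Effect of one such case.** The documents give no rate of missing more than 3 weeks of drug, so the size is stated per case. The loss in the estimate is 1/n. The limits assume that every other participant clears.

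| n | Loss in SVR12 | Lower limit, n of n | Lower limit, n − 1 of n |
|---|---|---|---|
| 50 (planned total) | 1/50 = 2.0 points | 92.9% | 89.4% |
| 60 (20 prospective + 40 retrospective) | 1/60 = 1.7 points | 94.0% | 91.1% |
| 20 (prospective arm alone, upper size) | 1/20 = 5.0 points | 83.2% | 75.1% |
| 10 (prospective arm alone, lower size) | 1/10 = 10.0 points | 69.2% | 55.5% |

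At n = 50 the lower limit moves by 92.9 − 89.4 = 3.5 points. The last two rows are an assumption about reporting: 4.1 plans combined and separate pre- and post-transplant estimates, not a separate SVR12 estimate for the prospective arm. The sizes of the pre- and post-transplant groups are not given.

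**The case against.** The strongest reply is that the protocol, read as a whole, already keeps this person in follow-up. The 9.2 lead-in is permissive: it gives a right to withdraw, not a duty. The list is not strictly about leaving the study, since item 5 speaks of discontinuing study drug. Section 7.10 names early termination in its heading, and its sentence on SVR visits is not confined to those who choose to stop. Section 7.7 and the footnote to the 11.1 schedule also provide an end-of-treatment visit for people who terminate early. On that view, removal leads to an end-of-treatment visit and then to the SVR visits if HCV RNA is undetectable.

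This stands as a possible reading, and it is why the point is a tension and not a proven contradiction. It does not close the matter. Item 3 itself says removal will happen, 9.2 separates its list from the stopping of treatment, and no sentence tells sites that SVR follow-up survives removal under item 3. The opening sentence of 7.10 also concerns participants who elect to stop, which fits removal for non-compliance poorly.

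A second reply is that 8.7 stops drug after more than 5 days, so item 3 would seldom be reached. That depends on gaps being noticed as they occur. On a 12-week course no visit is scheduled between Week 4 and Week 12, so one long gap may come to light late. The documents do not allow the frequency to be worked out either way.

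Two sections could be pressed too hard. A reader might infer that 8.9 directly contradicts item 3, but the sentence in question covers confirmed virologic failures. It shows a general intent to follow people off drug and no more. A reader might also take 4.4.1 as confirming that removed participants lose their SVR12 measurement, but that sentence only sets when the analysis is run.

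**Conclusion.** The point holds as a wording problem that is cheap to repair. Item 3, followed as written, can turn a measurable SVR12 success into an imputed failure, and the text does not settle whether 7.10 overrides it.

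The size is modest: 2 points per case at n = 50, with the exact lower limit going from 92.9% to 89.4%. This rests on one affected participant, on that participant having cleared HCV, on the site taking the literal reading, and on all others clearing. Only the 10 to 20 prospective participants can be affected. The case is probably uncommon, though no rate is given. The error lowers SVR12, which is the conservative direction for a single-arm estimate, and no hypothesis test or margin depends on it.

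Two stronger conclusions are not supported. A reader might infer that the primary result is materially biased, but nothing in the documents suggests more than an occasional case. A reader might also infer that the missed-visit half of item 3 does the same damage. On a 12-week course the visits after Day 0 are Weeks 4 and 12 and post-treatment Weeks 12, 24 and 36 (3.2, 7.6, 11.1), so a fifth miss comes after SVR12. On a 24-week course with the Week 16 and 20 visits of 7.6, a fifth miss before SVR12 requires missing all of Weeks 4, 12, 16, 20 and 24, which leaves no scheduled HCV RNA after Day 0. That limb needs no separate repair.

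Classification: cheap improvement.

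**What to change.** Reword the missed-drug part of 9.2 item 3 along these lines: if a subject misses more than 3 weeks (cumulative) of study drug, study drug is permanently discontinued; the subject stays in follow-up through the SVR12 and SVR24 visits counted from last dose, per section 7.10, unless consent is withdrawn.

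The cumulative limit should stand on its own and not cite 8.7, which deals with a single interruption. The missing-data rule in 4.3 stays as it is.

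The cost is a change of protocol wording and a few already scheduled visits in poorly adherent participants. Some of them will not attend, and they remain failures under 4.3 with or without the change.

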10 ADVERSE EVENT REPORTING AND MONITORING

10.1 Definitions

Adverse Event (AE): Any untoward or unfavorable medical occurrence in a human subject, including any abnormal sign (e.g. abnormal physical exam or laboratory finding), symptom, or disease, temporally associated with the subject's participation in the research, whether or not considered related to the research

Adverse Reaction (AR): An adverse event that is caused by a drug.

Suspected Adverse Reaction (SAR): An adverse event for which there is a reasonable possibility that the drug caused the adverse event. ‘Reasonable possibility’ means that there is evidence to suggest a causal relationship between the drug and the adverse event. A suspected adverse reaction implies a lesser degree of certainty about causality than adverse reaction, which implies a high degree of certainty.

Serious Adverse Event (SAE):

A Serious Adverse Event is an AE that results in one or more of the following outcomes:

- death
- a life threatening (i.e., an immediate threat to life) event
- an inpatient hospitalization or prolongation of an existing hospitalization
- a persistent or significant incapacity or substantial disruption of the ability to conduct normal life functions
- a congenital anomaly/birth defect
- a medically important event*
- Medical and scientific judgment should be exercised in deciding whether expedited reporting is appropriate in other situations, such as important medical events that may not be immediately life threatening or result in death or hospitalization but they may jeopardize the subject or may require intervention to prevent one of the other outcomes listed above.

Unexpected Adverse Event: An AE is unexpected if it is not listed in the package insert or is not listed at the specificity or severity that has been observed. It is the responsibility of the Sponsor to make this determination.

Serious and Unexpected Suspected Adverse Reaction (SUSAR): A SUSAR is a Suspected Adverse Reaction that is both Serious and Unexpected.

Unanticipated Problem (UP): Any incident, experience, or outcome that is

1. unexpected in terms of nature, severity, or frequency in relation to
 - a. the research risks that are described in the IRB-approved research protocol and informed consent document; package insert or other study documents; and
 - b. the characteristics of the subject population being studied; and
2. related or possibly related to participation in the research; and
3. places participants or others at a greater risk of harm (including physical, psychological, economic, or social harm) than was previously known or recognized. (Per the study sponsor, an adverse event with a serious outcome will be considered increased risk.)

Unanticipated Problem That Is Not An Adverse Event (UPnonAE): An incident, experience or outcome that is not associated with an adverse event which meets the 3 criteria of a UP. Examples include occurrences of breaches of confidentiality, accidental destruction of study records, and unaccounted-for study drug

Protocol Deviation:

Any change, divergence, or departure from the IRB approved study procedures in a research protocol. Protocol deviations are designated as serious or non-serious and further characterized as:

- Those that occur because a member of the research team deviates from the protocol.
- Those that are identified before they occur, but cannot be prevented.
- Those that are discovered after they occur

Serious Protocol Deviation: A deviation that meets the definition of a Serious Adverse Event or compromises the safety, welfare or rights of subjects or others.

Non-compliance: The failure to comply with applicable NIH HRPP policies, IRB requirements, or regulatory requirements for the protection of human subjects. Non-compliance is further characterized as

1. Serious: Non-compliance that:
 - a. Increases risks, or causes harm, to participants
 - b. Decreases potential benefits to participants
 - c. Compromises the integrity of the NIH-HRPP
 - d. Invalidates the study data
2. Continuing: Non-compliance that is recurring
3. Minor: Non-compliance that, is neither serious nor continuing.

10.2 Assessing Adverse Events

If a diagnosis is clinically evident, the diagnosis rather than the individual signs and symptoms or lab abnormalities will be recorded as the AE.

All grade 3 or higher AEs occurring from the time treatment starts on Day 0 and through the specified study follow-up period will be documented, recorded, and reported. The Investigator will evaluate all AEs with respect to Seriousness (criteria listed above), Severity (intensity or grade), and Causality (relationship to study agent and relationship to research) according to the following guidelines.

10.3 Severity Grading

Severity of AEs will be graded according to the “Division Of AIDS Table For Grading The Severity Of Adult And Pediatric Adverse Events” (Version 2.0, November, 2014).

Adverse Events not found in the Toxicity Table will be assessed for severity and classified into one of the categories below:

- **Grade 1 (Mild):** Event requires minimal or no treatment and do not interfere with the participant's daily activities.
- **Grade 2 (Moderate):** Event results in a low level of inconvenience or concern with the therapeutic measures. Moderate events may cause some interference with functioning.
- **Grade 3 (Severe):** Event interrupts a subject's usual daily activity or functioning and may require systemic drug therapy or other treatment. Severe events are usually incapacitating.
- **Grade 4 (Potentially Life threatening):** Events causing inability to perform basic self-care functions OR Medical or operative intervention indicated to prevent permanent impairment, persistent disability, or death.
- **Grade 5 (Death)**

10.4 Causality Assessment

Causality (likelihood that the event is related to the study agent) will be assessed from the time study dosing begins until 30 days following the last dose considering the factors listed under the following categories:

Definitely Related

- reasonable temporal relationship
- follows a known response pattern
- clear evidence to suggest a causal relationship
- there is no alternative etiology

Probably Related

- reasonable temporal relationship
- follows a suspected response pattern (based on similar agents)
- no evidence of a more likely alternative etiology

Possibly Related

- reasonable temporal relationship
- little evidence for a more likely alternative etiology

Unlikely Related

- does not have a reasonable temporal relationship
OR
- good evidence for a more likely alternative etiology

Not Related

- does not have a temporal relationship
OR
- definitely due to an alternative etiology

Note: Other factors (e.g., dechallenge, rechallenge) should also be considered for each causality category when appropriate. Causality assessment is based on available information at the time of the assessment of the AE. The Investigator may revise the causality assessment as additional information becomes available.

